Al muzian *et al.* 2017 (18) conducted meta-analysis to explore the effectiveness of nickel titanium closing springs and elastomeric power chains (EPC) in orthodontic space closure and to assess the adverse periodontal effects, cost efficiency and patient-centred outcomes between both of these methods, and they concluded that both of NiTi closing springs and elastomeric chains are efficient force delivery systems in closing extraction space with space closure being the resultant of anterior teeth retraction, anchorage loss or combination.

3) 3D digital model scanning and its reliability

El-Beialy and Mostafa Y.A. 2010 (19) compared the accuracy of dental measurements taken with calipers on 34 orthodontic plaster dental casts to those from computed tomography scans of the same dentition. The mesiodistal widths of teeth, arch widths, arch lengths, arch perimeters, and palatal depths were made with the calipers on a plaster cast. The patients were also scanned with computed tomography, and measurements were made digitally with 3DD, a 3-dimensional-based dental measurements program. The results showed high correlation between the conventional method and the 3DD in all the 3 planes of space. Thus, 3D dental measurement programs (such as the one used in this study) can be a valid alternative to conventional stone dental models.

Kim *et al.* 2016 (20) analysed the accuracy of Bolton analysis obtained from digital models scanned with Ortho Insight (3D) laser scanner system in comparison to those obtained from cone beam computed tomography (CBCT)

images and traditional plaster models. CBCT scans and plaster model's scans were obtained from fifty patients. Bolton ratios were calculated with the Ortho Insight 3D laser scanner software, CBCT scans were imported and analyzed using AVIZO software and plaster models were measured with a digital caliper. Laser scanned digital models were found to be highly accurate compared to physical models and CBCT scans for assessing the spatial relationship of dental arches for orthodontic diagnosis.

Database search:

A search was performed on electronic databases (PubMed, Cochrane library).

Aim of the study

A-PICOS format:

Population:

Adolescent and adult orthodontic patients requiring first premolars extraction.

Intervention:

En-masse retraction using sliding mechanics (friction) with mini screws used as anchorage.

Comparator:

Two-steps retraction using sliding mechanics (friction) with mini screws used as anchorage.

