Outcome measure:

	Outcome Name	Measuring Tool	Measuring Unit
Primary Outcome	Duration of space closure	Dental digital Model Records of visits	
- Scanned digital models in (mm)
o Models taken every montho Analysed using 3 Shape Software- computerized record system of the recruited patient (months, days, years)

Secondary Outcomes	Anchorage loss	Digital models	- Linear measurement in mm
	Pain	Pain scoring sheets given to patients	- VAS scoring from 1-10 ^(Fig 1)

B-Research question:

Will en-masse retraction offer shorter treatment duration compared to two steps retraction, in patients having maxillary protrusion?

Objectives of the study

Research hypothesis:

The null hypothesis (H_0) of this research is that there's no difference between both en-masse and two steps techniques on duration of retraction during en-masse and two steps retraction following 1st premolar extraction.

Primary objective:

Evaluating the duration of En-masse and two steps retraction using friction mechanics.

Secondary objectives:

Assessing the amount of anchorage loss, pain and discomfort during retraction. In addition to this, of anterior teeth will be measured following en-masse and two steps retraction using friction mechanics.

Study design:

This is a randomized clinical trial with two arms parallel group, and 1:1 allocation ratio. In one group, will receive frictional mechanics during En masse retraction, while the other group will receive frictional mechanics during two steps retraction. The duration of retraction will then be compared between both interventions.

Material and Methods

I) Participants, Interventions, and Outcomes

A] Study Setting:

The study will be performed in the clinic of the Orthodontic Department at the Faculty of Oral and Dental Medicine, Future University in Egypt. The recruited sample would be from the Egyptian urban and rural population.

B] Eligibility criteria:

Inclusion criteria: for the participants include the following:

1. Age range (14-24)
2. Adolescent & Adult patients (both genders)
3. Patients with maxillary protrusion requiring first premolars extraction (Bimaxillary Protrusion or Class II division 1 cases) as confirmed from lateral cephalometric, pre-treatment records & from clinical examination.
4. Patients with fully erupted permanent teeth (not necessarily including the third molar).
5. Cases requiring maximum anchorage during retraction.

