Our sample size calculation is based on a previous study comparing the effect of En masse versus two-steps using friction and frictionless mechanics²⁴. Using PS software output, we are planning a study of a continuous response variable from independent Group I and Group II subjects with 1 Group I(s) per Group II subject. In a previous study the response within each subject group was normally distributed with standard deviation 0.76. If the true difference in the Group II and Group I means is 1.0, we will need to study 10 Group II subjects and 10 Group I subjects to be able to reject the null hypothesis that the population means of the Group II and Group I are equal with probability (power) 0.8. The Type I error probability associated with this test of this null hypothesis is 0.05. Considering drop out a sample size 15 per group is appropriate.

G] Recruitment strategy:

The principal investigator will recruit the patients from the clinic of Orthodontic department, Faculty of Oral and Dental Medicine- Future University in Egypt. Screening of patients will continue until the total number of participants for the study is collected.

II) Assignment of interventions:

A] Sequence generation:

The supervisor of the study will apply Computer generated random numbers to randomly assign patients to group A (En-masse) or B (two steps) using Microsoft Office Excel 2007 sheet. The patient numbers will be written in the first column and the supervisor will select function RAND to generate the randomization

number in the second column. These numbers will be sorted according to the randomization number so the first column numbers will be randomly distributed.

B] Allocation concealment mechanism:

The Co-supervisor of the study ([name]) will write the randomization numbers of the patients on opaque white papers folded three times to form sealed envelopes and store it inside a box. The codes for randomization will be securely held at the secretary's office.

C] Implementation:

At the time of intervention, the main operator will send the patient to the secretary's office. Then, the assigned employee will open the box and ask the patient to select one envelope. The main operator will contact the supervisor to know the order and then the main operator will allocate each patient to assign each participant for the corresponding intervention either (En-masse or two steps group) according to the list of codes of randomization.

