- The specialized statistician will be responsible for the statistical analysis of the study by:
 1. Presenting the data as mean, standard deviation (SD) and Standard error (SE) values.
 2. Using Paired t-test to compare between the friction and the frictionless group of retraction as well as to compare between the pre-and post -treatment data for each group.
 3. Using Anova test to determine the rate of anterior segment retraction.
 4. Statistically evaluate the patient acceptance for both techniques.
- For this study, the specialized statistician will use IBM11 SPSS12 Statistics Version 20 for Windows to perform the required statistics.
- The significance level will be $P \leq 0.05$. Highly significant variables are detected when P value is less than 0.01.

Assessors Reliability:

- To achieve high reliability for measurements, the supervisor will choose a well-experienced inter-examiner during the study.
- A training session will be provided for the examiners to ensure standard measurements techniques.
- Each examiner will complete the measurements on a model and will repeat the procedure after one week to assess the intra- and inter-examiner reliability.
- The supervisor will compare the measurements of the two assessors for disagreement with a difference of more than one millimeter.
- The supervisor will evaluate the amount of variation in measurements among and between examiners to test the performance of each assessor.
- The examiner with less reliability will receive additional training but will be replaced during the study.
- The specialized statistician will calibrate the intra and inter-examiner reliability for the measurements of the study by the Intra-class correlation coefficient (ICC). The closer the ICC to 1.0, the higher reliability between assessors. According to Fleiss:" ICC values between 0.7 and 0.9 represent good reliability." The kappa scores between study examiners will be calculated, a range of 0.60-0.80 will represent acceptable reliability.

IV) Method Monitoring:

A] Data Monitoring: An independent Data Monitoring Committee (DMC) will monitor the results of the study. The Committee will include the trial's supervisors, who will periodically review the trial data and identify the need for any adjustments or modifications during the study.

B] Interim Analysis: no interim analysis will be performed during the study.

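### The only between-group test named is a paired t-test of friction versus frictionless groups, but the trial has two independent, unmatched arms that both use friction

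*Combined protocol and SAP*

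**What the plan says.** Section III-C] Statistical Analysis, item 2, gives the between-group test: "Using Paired t-test to compare between the friction and the frictionless group of retraction". The same sentence applies that test within arms, "as well as to compare between the pre-and post -treatment data for each group". Item 1 covers descriptive statistics, item 3 an ANOVA of the rate of anterior retraction, and item 4 patient acceptance.

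The rest of the document describes a different comparison:

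- The PICOS table of contents defines the intervention as "En-masse retraction using sliding mechanics (friction) with mini screws used as anchorage" and the comparator as "Two-steps retraction using sliding mechanics (friction) with mini screws used as anchorage".
- Study design: "This is a randomized clinical trial with two arms parallel group, and 1:1 allocation ratio", followed by "The duration of retraction will then be compared between both interventions".
- Section F] Sample size calculation is for "a continuous response variable from independent Group I and Group II subjects". It uses SD 0.76, difference 1.0, power 0.8 and type I error 0.05, which leads to 10 per group, raised to 15 for dropout.
- Section II-A] Sequence generation allocates individual patients by sorting spreadsheet random numbers. It describes no matching, and no split-mouth element appears anywhere.

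**The concern.** Item 2 is wrong in two separate ways.

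First, the test does not fit the design. A paired t-test needs a rule that links each en-masse patient to one two-step patient. The design supplies none, so the analyst would have to invent the pairs.

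Second, the groups named are not this trial's arms. Both arms use friction.

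Item 2 is the only place where a between-group test that could cover duration is named. Duration is also a single value per patient, so the sound within-arm part of the item does not apply to it. The statistician must either follow item 2, in which case the p-value depends on patient order, or override it, in which case the primary test is chosen outside the plan.

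**Working it through.** **Inputs** (section F): difference 1.0, SD 0.76 within each group, power 0.8, type I error 0.05. Sidedness is not stated; two-sided is assumed.

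**1. Reproduce the plan's figure.** For two independent means, n per group = 2 × [0.76 × (1.960 + 0.842) / 1.0]² = 9.07, rounded up to 10. This matches the stated 10 per group. The alternatives do not: a paired calculation taking 0.76 as the SD of differences needs 7 pairs, and a one-sided independent t-test needs 8 per group. The sample size therefore rests on a two-sided independent comparison, not on the test in item 2.

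**2. Power of each test.** The noncentral t distribution is used. If the pairing is arbitrary, the correlation within pairs is 0 and the SD of a paired difference is 0.76 × √2 = 1.075. The noncentrality parameter is then the same for both tests, 1.0 / (0.76 × √(2/n)). Only the degrees of freedom differ: 2n − 2 for the independent test and n − 1 for the paired test.

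| n per arm | Noncentrality | df, independent / paired | Power, independent | Power, paired |
|---|---|---|---|---|
| 10 | 2.94 | 18 / 9 | 79.5% | 74.5% |
| 11 | 3.09 | 20 / 10 | 83.5% | 79.4% |
| 12 | 3.22 | 22 / 11 | 86.9% | 83.5% |
| 15 | 3.60 | 28 / 14 | 93.5% | 91.7% |

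**3. Unequal arms** (assumed 14 and 11 completers). The independent test keeps all 25 patients: noncentrality 1.0 / (0.76 × √(1/14 + 1/11)) = 3.27, df 23, power 87.8%. The paired test can form only 11 pairs and discards 3 patients: power 79.4%.

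**4. Pairs fixed at the start** (a hypothetical procedure; the plan describes none). With 15 pairs and k random losses in each arm, the expected number of complete pairs is (15 − k)²/15. For k = 2, 3, 4 and 5 this is 11.3, 9.6, 8.1 and 6.7 pairs, and paired power is 80.5%, 72.1%, 62.1% and 50.9%. The independent test on the same completers has 89.6%, 86.9%, 83.5% and 79.5%. Five losses per arm is the whole of the plan's allowance (15 − 10).

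**5. Dependence on patient order.** In 4,000 simulated trials at the planned effect, each re-paired at random 400 times, a trial was counted as order-dependent if between 5% and 95% of its pairings were significant. That held for 33.8% of trials at 10 per arm, 23.6% at 12 and 12.5% at 15. With a stricter band of 20% to 80% (3,000 trials), the share is about 19% at 10 per arm and 8% at 15.

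**6. Type I error.** In 200,000 simulated trials with arbitrary pairing it was 4.9% at 10 pairs and 5.0% at 15.

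**The case against.** The strongest reply is that this is an internal contradiction with little practical consequence. The null hypothesis, the contrast and the independence of the groups are all written down elsewhere, and a specialist statistician will do the analysis. At 15 completers per arm even an arbitrary pairing costs only 93.5 − 91.7 = 1.8 points of power, and paired power stays above 80% down to 12 pairs. The larger losses rest on an assumed split of completers or on pairing in advance, which the plan does not contain. The order-dependence share also depends on the band chosen: a single random pairing disagrees with the independent test in only about 9% of trials at 10 per arm and 3.5% at 15.

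Much of this stands. The intended contrast is clear, the power loss at full enrolment is small, and the scenarios in steps 3 and 4 should not carry the argument. A further limit is that section F gives 1.0 and 0.76 without units and does not say that the response is duration. The power figures therefore illustrate the plan's inputs; they are not established for the primary outcome.

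None of this supplies a test. A clear contrast is not a specified analysis, and relying on the statistician to depart from item 2 means that the primary test is not prespecified.

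**Conclusion.** The concern holds and should be corrected before outcome data are analysed. Item 2 names a test that the design cannot support and groups that the trial does not have, and nothing else in the document specifies a test for duration. This conclusion comes from the text and does not depend on any numerical assumption.

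The size of the statistical harm does depend on assumptions: two-sided 5%, the section F inputs, and pairing unrelated to outcome. On these, the loss is 5.0 points of power at 10 per arm and 1.8 at 15, with more if the arms end unequal. The significance verdict also turns on the pairing in an appreciable minority of trials. False positives do not increase.

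**What to change.** Replace item 2 with wording such as: *Duration of space closure will be compared between the en-masse and two-step arms with an independent-samples (Welch) t-test, reporting the mean difference with its 95% CI. Other continuous outcomes that give one value or one change per patient will be compared in the same way. Paired t-tests will be used only for pre/post change within an arm.* Remove the reference to friction and frictionless groups. The pain VAS is recorded at each 4-weekly visit and should have its own line, because a single two-sample t-test may not suit it.

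The cost is one item of wording, plus a formal amendment under section V-B] if the protocol is already approved. No extra patients, visits or measurements are needed, and 10 per group raised to 15 stands. Using Welch rather than the pooled test costs about 0.4 points of power at 10 per arm (79.1% against 79.5%) and essentially nothing at 15 (93.5% for both). A pooled independent-samples t-test would also resolve the contradiction.

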6. Minimal crowding 2-3 mm.

Exclusion Criteria: for the involved subjects included:

1. Patients suffering from any systemic diseases interfering with tooth movement.
2. Patients with extracted or missing permanent teeth. (Except for third molars).
3. Patients with badly decayed teeth.
4. Patients with any parafunctional habits (i.e. Bruxism, tongue thrusting, mouth breathing, etc...).
5. Patients with previous orthodontic treatment.

C] Interventions:

➤ Medical History Questionnaire:

For every patient, to exclude the presence of any systemic condition interfering with orthodontic treatment.

➤ Clinical Examination:

Oral structures will be examined to identify caries, fracture or missing teeth. Gingival tissues will be carefully examined for any gingivitis, periodontitis, recession, or lesions.

➤ Diagnosis

Check the potential patient to fulfill the previously mentioned inclusion criteria. Every participant will be asked to sign an informed consent about the study. Full set of records (study models, panorama radiograph and lateral cephalometric radiographs, photos) will be taken for every patient as part of the routine procedure for treatment of patients in the clinic of the Orthodontic Department, Future University in Egypt.

➤ Clinical Procedure:

After taking pre-treatment records, every patient will receive:

- Miniscrews will then be placed in the upper arch between the second premolar and first molar.
- The patient will be referred for extraction of first premolars.

- Anchorage will be secured, followed by Leveling and alignment for the bonded and banded teeth through following the wire sequence: 0.014 NiTi, 0.016×0.022 NiTi and 0.017×0.025 StSt.
- Bonding of all teeth except for first premolars and banding/bonding the first and second molars will be done using Roth prescription brackets (0.022 x 0.028 slot)*.
- After leveling and aligning is completed (right before retraction), the patient will be referred for the uptake of pre-intervention records for en masse group (Impression for models, photos extra oral and intra oral and pain questionnaire).
- For two step group canine retraction will take place on a 0.017×0.025 StSt arch wire, once canine retraction stage is completed, the patient will be referred for the uptake of pre-intervention records.

➤ **Acquisition of pre-intervention records:**

- Alginate impressions will be taken before retraction (without the arch wire in place) followed by digital scanning of produced models.

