- Photos (Extra and intra oral).
- Pain questionnaire distributed with explanatory session on it.

➤ **Begin of Retraction:**

- Crimpable hooks added to the arch wire (0.017"x0.025" Stainless steel) distal to the lateral incisor passing near the center of resistance of the anterior segment.
- A ligature wire extending between the second premolar and miniscrews will be used for proper anchorage control.

- Retraction will start on a 0.017"x0.025" Stainless steel wire using elastomeric chain (force applied will be 200 g per side) (24) extending between the crimpable hooks and the molar hooks.
- The force will be measured by a force gauge and reactivated every 4 weeks maintaining constant force of retraction all over the retraction phase.

➤ **Follow up visits**

Patients will be asked to attend for follow up sessions every 4 weeks for:

- Evaluation of miniscrews stability.
- Replacement of the power chain to maintain a force of 200 gm per side for en masse group and 160 gm per side for two step group.
- Impression taking to assesses amount of space closure.
- Recording the pain scoring sheet.

➤ **Criteria for discontinuing or modifying the allocated intervention:**

In cases of prolonged swelling or pain related to the miniscrew, the patient will be given strict oral hygiene measures and may wait for three weeks before the beginning of retraction.

In cases of loose or broken miniscrews, the screw will be removed and replace the miniscrew after total resolution of the inflammation.

In case of non compliant patients.

□ **Post-retraction Questionnaire:**

The patients of both groups will be asked to fill in questionnaires regarding their experience with their allocated technique, during the whole retraction period from day of extraction till the end of retraction.

□ **Retraction records**

Following en-masse and two steps retraction, patients will be referred to the same radiology center to acquire the final cone-beam CT to assess the movement and inclination of anterior teeth.

The final dental model will be used to assess the rate of retraction and molar anchorage loss achieved throughout the study.

□ **Criteria of ending the retraction**

- Class I canine relation
- Normal overjet
- Balanced facial profile
- Closing extraction space

□ **Material Used**

- American Orthodontics Brackets, Roth prescription, 22 slot size.
- American Orthodontics Elastomeric power chains
- American Orthodontics Elastomeric O-ties
- American Orthodontics Ligature wire.

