- Miniscrew, 8 mm length x 1.6mm diameter TAD (Jeil).
- American Orthodontics Arch wires.
- American Orthodontics Molar bands/tubes.

D] Outcomes

[figure not shown]
Primary outcome: is to monitor the Duration of space closure during en-masse and two steps retraction. All outcomes will be assessed as the difference between T0 at the start of retraction and T1 after complete space closure.

Secondary outcomes: is to monitor the changes in the anterior teeth position (final anterior teeth tip, torque and vertical position), anchorage loss, presence of any root resorption and pain associated with the different methods used for retraction.

E] Participant timeline:

1. The principle investigator will screen the potential patients through careful clinical examination of patients at the orthodontic department, Faculty of Oral and Dental Medicine, Future University in Egypt.
2. All recruited patients should fulfil the previously mentioned inclusion and exclusion criteria.
3. Every participant will be asked to sign an informed consent before the beginning of the study.
4. After patient's enrolment, each participant will be asked for pre-intervention records to ensure proper diagnosis.
5. The principle investigator will randomly allocate the patients to one of the intervention groups.

6. Anchorage will be secured by placement of miniscrew, followed by extraction of the first premolar.
7. Active intervention will begin after proper levelling and alignment of the upper arch.
8. The principle investigator will take pre-retraction records for every participant T0.
9. Power chain is used for anterior segment retraction.
10. Each patient will come every 4 weeks for follow up visit, for appliance activation and uptake of impression for interim records + monitoring of recording the VAS sheet.
11. After complete space closure, the principle investigator will take post-retraction records for each participant T1.
12. Every patient will fill up a questionnaire regarding his experience during treatment.
13. The principle investigator will continue the normal treatment and achieve proper finishing for every patient after the end of the study.

F] Sample size calculation:

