Assignment to either intervention will occur before levelling and alignment stage.

D] Blinding:

Blinding of the operators: Blinding will not be possible for the operators during the application interventions and during the follow up visits. The principal operator is responsible for assigning subjects to interventions according to the concealed allocation, appliance activation at follow up visits, dental impressions and acquisition of dental casts.

Blinding of the outcome assessors: It is a single blinded study, therefore, only the outcome assessors will be blind. The patients name will be sealed from pre and

post radiographs and study models. Then two assessors will carry out, blindly and independently, the measurements and analysis of the study.

III) Data collection, management and analysis:

A] Data collection methods:

Primary outcomes:

1. Total Retraction Duration: to assess the timing of antero-posterior movement of anterior teeth and first molars, the principle investigator will take study models for every participant monthly during the follow up visits. Then will digitize the models and identify the landmarks, reference lines and planes on the pre, interim and post-retraction digital dental models for measurements reading. Also, by identifying the landmarks, reference lines and planes using CBCT taken before and after the completion of retraction.

Secondary outcome:

1. Anchorage loss: will be accessed by the principal investigator via CBCT taken before and after the completion of retraction by identifying the landmarks, reference lines and planes, then will interpret the measurements in degrees and millimeters.

2. Pain: Each patient will fill a questionnaire regarding his treatment experience in a VAS scoring from 1-10. The questionnaire will include several questions related to oral hygiene, pain and discomfort experienced throughout the trial.

B] Data management:

A colleague outside the research team will enter the data and organize it in excel sheets in the computer of the orthodontic department.

Data will include all photographs, models, radiographs and filled questionnaire.

C] Statistical Analysis:

- The principle investigator will be responsible for the extraction of the required data from the CBCT taken before and after retraction as well as the study models taken at every follow up visit. The data will be sent to a specialized statistician.

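### Separate pre/post paired t-tests in each arm cannot show whether the techniques differ on the secondary outcomes, and the rest of item 2 supplies no valid arm comparison

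*Combined protocol and SAP*

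**What the plan says.** - **Within-arm test.** III C (Statistical Analysis), item 2, second half: a paired t-test will "compare between the pre-and post -treatment data for each group".
- **Between-group test.** The first half of the same item reads "Using Paired t-test to compare between the friction and the frictionless group of retraction". Under the PICOS list and the study design, both arms use friction mechanics in a parallel 1:1 design.
- **Outcomes.** I D (Outcomes): "All outcomes will be assessed as the difference between T0 at the start of retraction and T1 after complete space closure". The secondary outcomes there are anterior tooth tip, torque and vertical position, anchorage loss, root resorption and pain. The primary outcome is a duration: "Primary outcome: is to monitor the Duration of space closure during en-masse and two steps retraction".
- **Randomisation.** End of II C (Implementation): "Assignment to either intervention will occur before levelling and alignment stage".
- **T0 records, en-masse arm.** I C, Clinical Procedure: "After leveling and aligning is completed (right before retraction), the patient will be referred for the uptake of pre-intervention records for en masse group".
- **T0 records, two-step arm.** Same section: "once canine retraction stage is completed, the patient will be referred for the uptake of pre-intervention records".
- **Content of the T0 records.** The list under Acquisition of pre-intervention records has impressions, photographs and, for pain, "Pain questionnaire distributed with explanatory session on it". It has no CBCT. III A (Data collection methods) nevertheless relies on CBCT both before and after retraction.

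**The concern.** The secondary question is whether en-masse and two-step retraction differ. A significant pre/post test in one arm and a non-significant one in the other is not evidence of a difference. Two significant tests say only that something changed in both arms, which is expected when teeth are being retracted.

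A statistician who follows item 2 literally would produce two within-arm P values per outcome and no valid arm contrast. Items 3 and 4 do not fill the gap: item 3 is an ANOVA for the rate of anterior retraction, and item 4 promises an evaluation of patient acceptance without naming a method. The risk is that readers take the within-arm P values as the comparison of techniques. That can suggest a difference where there is none, or hide one that exists.

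**Working it through.** **1. The plan's own figure.** The sample size section (I F) uses SD 0.76, difference 1.0, power 0.8 and alpha 0.05; two-sided testing is assumed here. The normal approximation gives n = 2 × (1.96 + 0.842)² × 0.76² / 1.0² = 9.07, so 10 per arm, as stated. The two-sample t-test has power 0.795 at 10 per arm and 0.935 at 15. This calculation is for independent groups, so the paired test in item 2 does not match it.

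**2. Same true change in both arms.** The arms are independent. If each within-arm test has power p, then P(exactly one arm significant) = 2p(1-p):
- p = 0.2 or 0.8: 2 × 0.2 × 0.8 = 0.32
- p = 0.5: 2 × 0.5 × 0.5 = 0.50, the maximum

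To put this on the trial's scale, assume that the SD of the change is 0.76. The documents give neither the unit of that SD nor the quantity it describes. Power of the paired t-test comes from the noncentral t distribution.

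| True change in both arms | Power, n = 10 | One arm only | Power, n = 15 | One arm only |
|---|---|---|---|---|
| 0.4 | 0.319 | 43% | 0.475 | 50% |
| 0.5 | 0.459 | 50% | 0.659 | 45% |
| 0.75 | 0.793 | 33% | 0.944 | 11% |
| 1.0 | 0.958 | 8% | 0.997 | 0.6% |

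**3. A real difference.** Take true changes of 1.0 and 2.0, which differ by the design value of 1.0, with the same SD. Both within-arm tests are significant with probability 0.96 at 10 per arm and 0.997 at 15. The within-arm results then look alike, while an independent two-sample test detects the difference with power 0.795 or 0.935.

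**4. Can T0 serve as a covariate?** Set the sections in order of time:
- Allocation comes before levelling and alignment (II C), so T0 is after randomisation in both arms.
- In the en-masse arm the T0 records come before any retraction. In the two-step arm they come after canine retraction (I C).
- I D places T0 at the start of retraction, which does not agree with the two-step schedule in I C.

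T0 in the two-step arm can therefore already carry an effect of the allocated treatment. Adjusting for it could bias the arm difference.

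**5. What adjustment could gain.** With a true baseline, equal variances at both times and correlation r, the variance ratio of the baseline-adjusted to the change-score comparison is (1-r²)/(2(1-r)) = (1+r)/2. For assumed r of 0.3, 0.5, 0.7 and 0.9 this is 0.65, 0.75, 0.85 and 0.95. Estimating the slope with 10 per arm multiplies these by about 1 + 1/(20-4) = 1.06, giving about 0.69, 0.80, 0.90 and 1.01. The documents give no r, so the gain lies anywhere from about 31% to nothing over this range. None of it applies to T0 as now defined.

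**The case against.** The strongest reply is that a between-group comparison is already intended in the same sentence, and that I D defines every outcome as a T0–T1 difference. On this reading the plan compares changes between arms and merely adds within-arm tests. Nothing says that the investigators will infer a difference from discordant P values, and discordance is rare when the true change is large (8% at 10 per arm for a change of 1.0).

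Much of this stands, and it rules out several stronger readings:
- A reader might infer that no arm comparison is planned. One is intended, but its test and its group names do not fit this trial, so it cannot be run validly as written.
- A reader might infer that T0 is collected and then wasted. It is not: T0 enters the outcomes as change scores.
- A reader might infer that adding T0 as a covariate is the ready remedy and needs no new data. The timing of T0 in the two-step arm makes that unsafe. A pre-retraction CBCT is missing from the list of records, and distributing a pain questionnaire with an explanation does not establish that a T0 pain score is recorded.
- A reader might infer that the investigators plan to use discordant P values as evidence. The documents do not say so. The 2p(1-p) figures show why such a reading must be barred.

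The reply does not supply a valid between-arm analysis for the secondary outcomes.

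**Conclusion.** The point holds for the secondary outcomes. The within-arm tests cannot compare the techniques, and the between-group half of item 2 does not make up for this. With equal true changes, the chance of exactly one significant arm is at most 50%; how close it comes depends on the within-arm power. The bound itself needs only independent arms with equal power. The tabulated figures also rest on the assumed SD of change.

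The sample size is unaffected, and so is the primary outcome on this point, since a duration has no baseline value. The use of a paired test between independent arms is a separate defect that reaches further.

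The timing of T0 matters beyond covariate adjustment. While T0 follows canine retraction in one arm only, the T0–T1 changes cover different parts of treatment in the two arms, so even a correct two-sample test of those changes would be hard to interpret.

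**What to change.** 1. In III C, item 2, report within-arm pre/post figures as description only, without P values.
2. For each secondary outcome, prespecify one independent between-arm difference with its 95% CI, using one value per patient (for example the mean over the measured teeth or sides). For pain, which is scored at repeated visits, state which score or summary is that value. If root resorption is recorded as present or absent, use a difference in proportions.
3. Before these analyses are fixed, reconcile I C (Clinical Procedure and Acquisition of pre-intervention records), I D, I E and III A on when T0 is taken in each arm and on whether a pre-retraction CBCT and a pain score exist.
4. Do not adjust for T0 as now defined. Any covariate should come from the diagnostic records that the participant timeline (I E, items 4 and 5) places before allocation: study models, lateral cephalogram and panoramic radiograph, where they measure the outcome.

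Cost: a few lines in III C, all within the named software, and one degree of freedom for each model with a covariate. Step 3 needs a protocol clarification. Whether it also requires records not now listed cannot be judged from the documents. The precision gained by adjustment is unknown and should not be counted on.
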